4 STUDY DESIGN

4.1 General Description

This study is a multi-center, randomized, open-label clinical trial evaluating the efficacy and safety of ESG as an adjunct to life-style intervention for weight loss and improvement in obesity-related co-morbidities compared to lifestyle intervention alone in participants with a BMI ≥ 30 and ≤ 40 kg/m² who have failed to achieve and maintain weight loss with a non-surgical program.

Participants will be recruited from outpatient clinical weight loss clinics and from study-related institutional review board (IRB) approved advertisements. The cohort will include nor more than 50 patients without at least one of a) hypertension (HTN) on one or more anti-hypertensive medications or b) type II diabetes mellitus (DM) on oral agents only with HbA1c ≤ 9 . Enrollment will be tracked continuously and enrollment closed to non-DM, non-HTN patients after meeting the target for that group.

Two hundred eligible participants will be stratified into three groups (obesity, obesity-hypertension, and obesity-diabetes) and then block-randomized 1 to 1.5 to treatment (80 participants) and control (120 participants) groups alone as depicted in the diagram on page 16. All treatment group participants will undergo endoscopy and those without endoscopic contraindications will undergo the ESG. All control subjects will follow a low-calorie, healthy lifestyle intervention only for 12 months. After 12 months of lifestyle intervention, eligible control participants will crossover to receive the ESG. Those who had the ESG will undergo a repeat upper endoscopy at 52 weeks +- 4 weeks to evaluate the durability of the plications and re-tighten the ESG if needed with continued follow-up for 12 additional months.

The study will have two levels:

1. Level 1: the randomized study phase with primary outcomes for both groups evaluated at 12 months
2. Level 2: the crossover, non-randomized study phase with outcomes for a) the initial treatment group at 24 months post ESG (12 months after the re-tightening procedure) b) for the controlled cross-over group evaluated at 12 months after ESG

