5.4 Randomization

Participants will be stratified to three groups (Obesity, Obesity HTN, and Obesity DM) and will be randomly assigned to treatment or control group with a 1:1.5 allocation per a computer generated randomization using variable block randomization.

Participants will be notified of their randomization assignment on the day of the randomization visit. Participants randomized to the control group will proceed to an appointment with the dietitian for their Week 1 visit on the day of randomization. Participants randomized to the treatment group will proceed to a brief visit with the dietitian to review the post-op liquid diet, and the ESG will be scheduled within 30 days of randomization. Participants of child-bearing potential will be required to have a pregnancy test within 7 days of the scheduled ESG.

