5.5 Trial Intervention

5.5.1.1.1 Control group

Participants randomized to the control group (lifestyle intervention only) in Level 1 will undergo a standard moderate intensity life-style intervention during the first 12 months of Level 1. The first dietary visit will be scheduled on the day of randomization. A low-calorie diet plan will be reviewed with each participant and will be adjusted according to each participant's needs. Participants in the control group will not undergo the liquid transitional diet as it is difficult to achieve compliance without intervention. Physical activity, including 150 minutes of aerobic exercise per week, will be encouraged and assessed for compliance during the study. Participants will have 12 follow-up visits in the 12 months of Level 1 as described in the schedule of events. Participants will receive \$100 for every 4 visits they attend consecutively in Level 1 with the ability to earn a maximum of \$300 at the end of the first 12 months of Level 1.

Control group participants who were compliant with at least 75% of visits in the first 12 months of Level 1, have not achieved $\geq 25\%$ EWL measured at the week 52 visit, or still have a BMI ≥ 30 and ≤ 40 , and have no new psychosocial contraindications as deemed by the treatment team to the procedure will cross over to receive ESG in Level 2, in addition to the standard moderate intensity lifestyle intervention program for 12 months. After crossing over into Level 2, participants will be able to earn the same remuneration as in Level 1 (\$100 for every 4 consecutive visits attended). Those who were compliant with attending 75% of the visits in Level 2 (second 12 months) will receive a bonus of \$300 at the final study visit, for a potential total of \$900 earned in the two years.

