TABLE 2. MERIT SCHEDULE OF EVENTS (Year 2, Level 2, Treatment Group, 80 Patients)							
	ESG retightening [†]	Post-Op Clinical Eval ^{**}	Follow-up after ESG retightening OR Week 60 [†]	Week 72-76*	Weeks 80, 88, 96	Week 104 (Final Year 2 visit)	Unscheduled Visit
Visit Number	17	-	18	19	20, 21, 22	23	
Informed consent							
Complete Physical Exam (CPE) by Investigator or Investigator delegated / medically qualified team member				X		X	X
Investigator or Investigator delegated/medically qualified team member exam			X	X	X	X	X
EKG if (> 50 yo)							
Formal nutritional assessment							
Formal psychology evaluation							
Pregnancy test (females of childbearing potential only)							
Laboratory tests ^{**}				X		X	
Questionnaires [#]				X		X	
Inclusion/exclusion criteria							
Endoscopy / Procedure	X						
Procedure Assessment Form	X						
GERD Questionnaire + Activity Assessment Form			X	X	X	X	
Weight, BMI/height, Waist and Hip Circumference Form	X		X	X	X	X	X
Vital Signs Form	X		X	X	X	X	X
Adverse Events Form		X	X	X	X	X	X
Medications Form ^{##}			X	X	X	X	X
Post-enrollment Nutrition / Exercise / satiety counseling and assessment			X	X	X	X	
Subject Satisfaction Questionnaire (study termination)						X	

** Electrolytes, Creatinine, CBC, Iron, TIBC, B12, 25-hydroxy Vitamin D, TSH, HgA1c, fasting blood sugar and insulin, PTT, fasting lipids profile (total cholesterol, LDL, HDL, and Triglyceride), ALT, AST, ALK-P, total bilirubin, direct bilirubin, BUN, total protein, albumin, CRP, urinalysis; also include PYY-1, GLP-1 and total Ghrelin pending sites' availability to analyze

IWFQOL-Lite, SF36, PHQ9, Pittsburg Sleep Quality Index (PSQI), Three factor eating questionnaire (TFEQ)

Record all medications including dose and frequency; especially diabetes and blood pressure medication.

++ Post-op phone call, no clinic visit, to occur between 18-36 hours post-op

+ ESG retightening to occur between Weeks 52-60 for those who qualify with in-clinic follow-up visit to occur 4 weeks post retightening, or subjects to continue to Week 60 for those who do not qualify for ESG retightening

*Lab draw to occur between Week 72-76

5.6.1.1.3 Schedule of Events for Control Group, Crossover in Year 1, Level 1

TABLE 3. MERIT SCHEDULE OF EVENTS (Year 1, Level 1, Control Group, 120 patients)									

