	Enrollment; Screening/ Baseline	Randomization / Week 1 visit	Weeks 4, 8	Week 12	Weeks 16, 20	Week 24 (6 month)	Weeks 30, 36, 42, 48	Week 52 (Final Year 1 visit), re-screen for crossover to ESG	Unscheduled Visit
Visit Number	-1	1	2,3	4	5,6	7	8,9,10,11,	12	
Informed consent	X								
Complete Physical Exam (CPE) by Investigator or Investigator delegated / medically qualified team member	X			X		X	X	X	X
Investigator or Investigator delegated/medically qualified team member exam		X ⁺⁺	X	X	X	X	X	X	X
EKG if (> 50 yo)	X							X	
Formal nutritional assessment	X								
Formal psychology evaluation	X								
Pregnancy test (females of childbearing potential only)	X								
Laboratory tests, H-pylori breath testing (baseline only)* *	X							X	
Questionnaires#	X			X		X		X	
Inclusion/exclusion criteria	X							X	
Endoscopy / Procedure									
Procedure Assessment Form									
GERD Questionnaire + Activity Assessment Form	X	X	X	X	X	X	X	X	
Weight, BMI/height, Waist and Hip Circumference Form	X	X	X	X	X	X	X	X	X
Vital Signs Form	X	X	X	X	X	X	X	X	X
Adverse Events Form		X	X	X	X	X	X	X	X
Medications Form##	X	X	X	X	X	X	X	X	X
Post-enrollment Nutrition / Exercise / satiety counseling and assessment		X	X	X	X	X	X	X	
Randomization to ESG vs. LS ⁺		X							
Subject Satisfaction Questionnaire (control phase)								X	

** Electrolytes, Creatinine, CBC, Iron, TIBC, B12, 25-hydroxy Vitamin D, TSH, HgA1c, fasting blood sugar and insulin, PTT, fasting lipids profile (total cholesterol, LDL, HDL, and Triglyceride), ALT, AST, ALK-P, total bilirubin, direct bilirubin, BUN, total protein, albumin, CRP, urinalysis; also include PYY-1, GLP-1 and total Ghrelin pending sites' availability to analyze

Eating disorder questionnaire + hospital anxiety and depression questionnaires (only at base-line), IWFQOL-Lite, SF36, PHQ9, Pittsburgh Sleep Quality Index (PSQI), Three factor eating questionnaire (TFEQ)

Record all medications including dose and frequency; especially diabetes and blood pressure medication.

+ LS start with the week 1 visit with no transitional diet.

++ Required only for Week 1 visit

5.6.1.1.4 Schedule of Events for Control Group, Crossover in Year 2, Level 2

[figure not shown]
TABLE 3. MERIT SCHEDULE OF EVENTS (Year 2, Level 2, Control Group, cross-over 120 patients)									
	ESG Procedure	Post-Op Phone Call	Weeks 1, 4, 8	Week 12	Weeks 16, 20	Week 24 (6 month)	Weeks 30, 36, 42, 48	Week 52 (Final Year 1 visit)	Unscheduled Visit
Visit Number	0	-	1,2,3	4	5,6	7	8,9,10,11	12	

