Informed consent for cross-over procedure									
Complete Physical Exam (CPE) by Investigator or Investigator delegated / medically qualified team member				X		X	X	X	X
Investigator or Investigator delegated/medically qualified team member exam			X	X	X	X	X	X	X
EKG if (> 50 yo)									
Pregnancy test (females of childbearing potential only)									
Laboratory tests **						X		X	
Questionnaires#				X		X		X	
Endoscopy / Procedure	X								
Procedure Assessment Form	X								
GERD Questionnaire+ Activity Assessment Form			X	X	X	X	X	X	
Weight, BMI/height, Waist and Hip Circumference Form	X		X	X	X	X	X	X	X
Vital Signs Form	X		X	X	X	X	X	X	X
Adverse Events Form	X	X	X	X	X	X	X	X	X
Medications Form##	X	X	X	X	X	X	X	X	X
Post-enrollment Nutrition / Exercise/ satiety counseling and assessment			X	X	X	X	X	X	
Subject Satisfaction Questionnaire (treatment phase)								X	

** Electrolytes, Creatinine, CBC, Iron, TIBC, B12, 25-hydroxy Vitamin D, TSH, HgA1c, fasting blood sugar and insulin, PTT, fasting lipids profile (total cholesterol, LDL, HDL, and Triglyceride), ALT, AST, ALK-P, total bilirubin, direct bilirubin, BUN, total protein, albumin, CRP, urinalysis; also include PYY-1, GLP-1 and total Ghrelin pending sites' availability to analyze

Eating disorder questionnaire+ hospital anxiety and depression questionnaires (only at baseline), IWFQOL-Lite, SF36, PHQ9, Pittsburgh Sleep Quality Index (PSQI), Three factor eating questionnaire (TFEQ)

Record all medications including dose and frequency; especially diabetes and blood pressure medication.

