7.2.2 Secondary Aims

Continuous secondary outcomes, including change in systolic and diastolic blood pressure and change in HbA1c, QOL questionnaires such as the SF-36, PHQ-9, and eating behavior scores will be compared between treatment arms using ANCOVA with adjustment for the same variables specified in the primary analysis.

Binary outcomes, including proportion with $\geq 25\%$ reduction in %EWL and incidence of esophagitis will be compared between treatment arms by Pearson Chi-square test.

Among patients randomized to the treatment ESG group, the association between the durability of plication at repeat endoscopy (score ≥ 1 on EGD grading system) and number of sutures required for re-tightening with change in EWL from 12 months to 24 months will be assessed using linear regression with adjustment for BMI, %EWL between randomization and 12 month follow up, HTN status, and DM status. This is an observational comparison.

Among patients randomized to the control LS arm, the percent EWL from the 12 month assessment to the 24 month assessment will be measured. This percentage will be compared to percent EWL in the same group with lifestyle intervention only in the first 12 months using a one sample t-test.

Among all subjects, %EWL will be compared at 24 months between initial and delayed ESG. However, this is not considered a comparison of randomized arms as follow up is not continued for patients with $\geq 25\%$ EWL from LS at 12 months.

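### Crossover visits are counted from the ESG procedure, but section 7.2.2 measures weight loss from month 12 to month 24, so weight change between the week-52 re-screen and ESG is counted with the ESG effect

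*Combined protocol and SAP*

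**What the plan says.** The combined protocol and SAP describes the crossover outcome on two clocks.

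**Counted from the procedure.** Section 4.1 has Level 2 outcomes "for the controlled cross-over group evaluated at 12 months after ESG". The crossover schedule (5.6.1.1.4) agrees: the procedure is visit 0 and the last visit is week 52 after it. The row "Weight, BMI/height, Waist and Hip Circumference Form" is marked on the procedure day, so an ESG-day weight will exist.

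**Counted from randomization.** In section 7.2.2, for patients randomized to lifestyle, "the percent EWL from the 12 month assessment to the 24 month assessment will be measured". The same section compares initial with delayed ESG at 24 months. The last secondary endpoint in 4.2.1 also names %EWL at 24 months for this group.

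**When crossover ESG happens.** Section 4.1: "After 12 months of lifestyle intervention, eligible control participants will crossover to receive the ESG". Section 5.5.1.1.1: controls who qualify "will cross over to receive ESG in Level 2, in addition to the standard moderate intensity lifestyle intervention program for 12 months". The control-arm schedule heads its last column "Week 52 (Final Year 1 visit), re-screen for crossover to ESG". The other ESG procedures have stated windows. For the treatment group, "the ESG will be scheduled within 30 days of randomization" (5.4), and the year-2 schedule has "ESG retightening to occur between Weeks 52-60 for those who qualify". The readable text states no window for crossover ESG.

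**The concern.** The two clocks agree only if ESG is done on the date of the week-52 visit. That visit is where eligibility for crossover is reassessed, with laboratory tests, so the procedure has to follow it. No visit is scheduled between it and crossover visit 0.

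Two things follow. First, any regain or loss between the month-12 weight and the procedure enters the interval that 7.2.2 treats as the response to ESG. The crossover cohort has no concurrent control in year 2, so nothing cancels that change. Second, the final weight is either 12 months after ESG and later than month 24, or at month 24 and less than 12 months after ESG.

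At stake are a listed secondary endpoint, the comparison of second-year with first-year weight loss, and the descriptive comparison of initial with delayed ESG. Section 7.1 also gives the crossover cohort its own hypothesis and power figure.

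**Working it through.** **1. The plan's own figure.** Section 7.1 states a one-sample t-test with n = 70, SD 30, two-sided alpha 0.05, an effect of 25% EWL and a reference value of 10%. The difference is 25 − 10 = 15 and the noncentrality is (15/30) × √70 = 4.18. Power from the noncentral t with 69 df is 98.5%, which agrees with the stated 98%. (A reference value of 0 would give over 99.9%, so the plan's figure does use 10%.)

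**2. When the last weight is taken.** Weeks from randomization = 52 + wait + 52. The documents give no waiting times; these are assumptions.

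| Assumed wait | Final crossover visit | Time since ESG if weighed at week 104 |
|---|---|---|
| 0 | week 104 (24.0 months) | 52 weeks |
| 30 days | week 108.3 (25.0 months) | 47.7 weeks |
| 8 weeks | week 112 (25.8 months) | 44 weeks |
| 12 weeks | week 116 (26.8 months) | 40 weeks |

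The two-week visit window in 5.5.1.1.2 absorbs a wait of up to two weeks. It applies to follow-up visits, not to the procedure.

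**3. What 1 kg is worth.** Excess weight = (BMI − 25) × height². The ideal BMI of 25 is from section 2.3 and the BMI range from the eligibility criteria. Height 1.70 m is an assumption (1.70² = 2.89).

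| Enrolment BMI | Excess weight | 1 kg in %EWL points |
|---|---|---|
| 30 | 5 × 2.89 = 14.45 kg | 6.9 |
| 35 | 10 × 2.89 = 28.90 kg | 3.5 |
| 40 | 15 × 2.89 = 43.35 kg | 2.3 |

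**4. Effect on the 7.1 test, if it starts at month 12.** Section 7.1 does not give the start weight, so this is conditional. At BMI 35, with an assumed mean regain before ESG and n and SD unchanged:

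| Mean regain | Remaining difference | Power |
|---|---|---|
| 0 kg | 15 | 98.5% |
| 0.5 kg | 15 − 1.73 = 13.27 | 95.4% |
| 1 kg | 15 − 3.46 = 11.54 | 88.7% |
| 2 kg | 15 − 6.92 = 8.08 | 60.3% |

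Loss during the wait shifts the estimate by the same amounts in favour of ESG.

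**5. A yardstick for these drifts.** Section 7.1 assumes 10% EWL over 12 months on lifestyle alone, or 10/12 = 0.83 points a month. At that pace, shifts of 1.73, 3.46 and 6.92 points take about 2, 4 and 8 months. That rate is loss under active treatment, so it gives scale only. It does suggest that the 2 kg row is an extreme case.

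**6. Starting at the ESG-day weight.** The waiting-period change drops out, and under the plan's assumptions power stays at 98.5%.

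**The case against.** The strongest reply is that prompt crossover was plainly intended. Section 4.2.1 speaks of ESG at 12 months, 7.1 of offering it at 12 months, and 5.5.1.1.1 treats Level 2 as the second year. With a wait of two weeks or less the label error is negligible. This stands as evidence of intent. It sets no limit, and it does not settle the start weight.

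A reader might infer that the wait is open-ended. The documents do not support that. The timeline figure (5.2) and the study flow (5.6.1.1.5) are not shown and may carry a window, and the readable text points to crossover near month 12. A missing window alone would be a matter of detail; the point is the conflict between the two clocks.

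A reader might also set the 30-day rule in 5.4 against the silence in 5.5.1.1.1 and call it a contradiction. It is not: that rule covers the treatment group only.

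Nor do the documents show that the 98% power is wrong. It belongs to a test against a fixed 10% whose start weight is unstated. The month-12 start comes from 7.2.2, whose test is against the same group's first-year result and has no stated power. Joining them is an inference, and the drifts are assumed.

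Finally, the randomized arm is also measured from randomization, with ESG up to 30 days later, and a month-12 start gives contiguous before-and-after intervals. Both are fair reasons to keep the total from month 12 in the report. They do not make it a clean post-ESG change, because in the randomized comparison both arms share the time origin, while the crossover analysis has no parallel arm.

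The added harm to the initial-versus-delayed comparison is small. That comparison already contrasts about 24 with about 12 months since ESG, and 7.2.2 says it is not randomized.

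**Conclusion.** The point holds as a mismatch of time origin and start weight. Section 4.1 and the crossover schedule count from the procedure; 4.2.1 and 7.2.2 name month 24, and 7.2.2 starts at month 12. Any weight change between the week-52 re-screen and ESG is counted with the ESG effect, and the final weight is late by exactly the wait.

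The direction of the bias is unknown and its size cannot be derived from the documents. Each kg of mean drift is worth 2.3 to 6.9 %EWL points across BMI 40 to 30 at the assumed height. The conditional power of about 95% or 89% needs a mean regain of 0.5 or 1 kg at BMI 35 and a month-12 start for the 7.1 test. The 60% figure is an extreme case, not an expectation.

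The primary 12-month randomized comparison is untouched. This is a modest correction to non-randomized analyses, best made before they are run so that the start weight is not chosen after the data are seen.

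**What to change.** In sections 4.2.1 and 7.2.2:

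- Name the crossover outcome as 12 months after ESG, as section 4.1 already does, and reconcile the sections on the time point.
- Report the crossover change in two parts on the same enrolment excess weight: (a) week-52 visit to the ESG-day weight at crossover visit 0; (b) ESG-day weight to week 52 after ESG. Use (b) as the post-ESG change. Report (a), the waiting time and the total from month 12 beside it.

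In section 7.1, state the start weight of the one-sample test.

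Whether a time window applies to crossover ESG is for the sponsor to decide and state.

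The cost is some SAP wording and a little more analysis on weights already scheduled; no new visit or patient is needed. One small downside is that the ESG-day weight may reflect short-term change just before the procedure, which is why part (a) and the total are reported with it.

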5.5.1.1.2 Treatment Group

ESG is an endoluminal procedure similar to sleeve gastrectomy targeting the shape of the stomach. The targeted shape is tubular gastric body with a small pouch in the fundus. A step-by-step video circulated to all sites and a mandate to have the proctor present for the first case were done to ensure conformity to the technique. The same expert endoscopist will proctor all sites. In general, the technique involves 7-9 bites in a running O shaped pattern that is repeated 4-5 times in the stomach to achieve the desired shape. Proximally, it might be difficult to do the O sequence; thus, the operator can do triangular 3-4 bites interrupted suturing sequence. Each O sequence can be enforced by a layer of triangular interrupted suture. All bites are intended to be full thickness with the aid of tissue helix. The re-enforcing bites can be submucosal. The sequence is staggered to avoid gaps. In general, sutures used is limited to 10. ESG narrows the stomach axially and reduce its length longitudinally.

Participants assigned to the treatment group will report to the procedure suite within 30 days of randomization. Participants of child-bearing potential will be required to have a pregnancy test within 7 days of the scheduled ESG. Participants taking medications for hypertension and/or type II diabetes will be instructed to notify their prescribing physician of their procedure and to discuss any necessary medication changes for the post-op period.

The ESG is done in the outpatient setting. Within two hours prior to ESG, IV access will be obtained, IV hydration initiated, and a transdermal scopolamine patch placed for patients 50 years of age or younger (this will be removed in 24 to 48 hours after the procedure).

Prior to ESG, a standard upper endoscopy is performed to rule out any contraindicating findings. All ESG procedures will be done under general anesthesia with endotracheal intubation and utilizing CO₂ insufflation. During the procedure, IV hydration will be continued and patients will be given the following: one dose of IV antibiotics (Zosyn, Ceftriaxone, or Ciprofloxacin), 8mg of IV Zofran, and 8mg of Decadron. A minimum of two liters of IV hydration (either normal saline or lactate ringers) should be administered in the perioperative recovery period before discharge. Sequential compression devices (SCDs) will be used perioperatively to decrease the risk of deep vein thrombosis (DVT) and pulmonary embolism (PE).

Patients will be prescribed the following medications after the procedure to manage expected post-procedural symptoms:

- Zofran 4mg rapid dissolving pills taken every 6 hours as needed for nausea for 7 days
- Phenergan 25mg suppositories taken twice daily as needed for nausea for 7 days
- Low dose liquid narcotic taken every 6 hours as needed for pain for 5 days
- Omeprazole 40mg capsule to be opened in apple sauce for the first 7 days after ESG, then taken as whole capsule daily for 12 months from date of ESG
- Ativan 0.5 mg taken orally once daily for up to 3 days as needed for intractable nausea or anxiety.

Admission for a 23 hours observation for symptom management is optional but permissible. All ESG patients will be given instructions prior to being discharged from the facility to help manage post-procedural symptoms, including nausea, vomiting and/or abdominal pain. Study staff will call patients once between 18-36 hours after the procedure to assess symptoms and to relay any issues to the PI. If the PI feels it is necessary to see a patient in clinic, an unscheduled visit will be scheduled appropriately.

All patients undergoing ESG will go on a 6 weeks transitional diet consisting of 4 weeks of full liquid protein shakes and 2 weeks of soft pureed diet (Appendix G). The transitional diet is designed to allow suture healing and incorporation within the plicated gastric wall. After the transitional diet period, all patients will be on a low-calorie healthy diet personalized by the dietician according to individual patients' needs and conducive to weight loss. Physical activity, including 150 minutes of aerobic exercise per week, will be encouraged and assessed for compliance during the study. It may be recommended for patients to take two chewable multivitamins and one calcium plus vitamin D supplement daily starting within 1 week of the ESG.

ESG patients will undergo a standard moderate intensity life-style intervention administered over 12 visits in the first year after ESG. Participants will be required to follow up with their prescribing physician to make any necessary changes to their hypertension and/or type II diabetes medications at 3, 6, 9 and 12 months. Completion of patient follow-up with providers for medication adjustment will be captured with completion of the appropriate CRF at the corresponding visits. In the event that participants are unable to contact their physician or participants are experiencing symptoms related to the medication dosing requiring urgent action, the study team will make any necessary

changes in their medication dosing and document these changes appropriately in the relevant CRFs. Any medication changes will be monitored and recorded by the study team.

All ESG patients in Level 1 (80) will be evaluated for %EWL at the end of Level 1 (measurement of primary endpoint). Those ESG patients who have achieved >25% EWL at the end of Level 1 will not undergo a repeat endoscopy and will continue to follow-up with a lifestyle intervention in Level 2. Those ESG patients who have not achieved >25% EWL at the end of Level 1 will undergo a repeat upper endoscopy at 52 to 60 weeks to assess the durability of the plications (see Plication Durability form), and perform a retightening of the ESG if needed. The need for re-tightening will be determined by the PI after evaluating the sutures based on a grading system presented in the retightening CRF. The retightening procedure will be performed if at least one of the three portions (proximal, mid, and distal) of the endoscopic sleeve is non-tubular in shape. For each tubular third of the sleeve, 1 point will be given. A score of 3/3 means the entire (proximal, mid, and distal) sleeve is tubular in shape. A score of 2/3 means that one-third of the sleeve is no longer tubular. A score of 1/3 means that two-thirds of the sleeve are no longer tubular. Finally a score of 0/3 means the entire sleeve is no longer tubular. Re-tightening will occur for patients with a score of 0, 1 or 2.

The retightening procedure will be performed in a similar fashion as the initial ESG with similar technique, peri-procedural care, transitional diet, and aftercare. However, the retightening procedure will only target open (non-restrictive) portions of the ESG; it should thus be an abbreviated procedure. The number of sutures used in the retightening procedure will be determined by the PI with the goal of re-capturing the tubular configuration of the sleeve.

All patients will continue follow-up with a modified lifestyle intervention program administered over 6 visits in the second year. Laboratory testing will be obtained as detailed in the study schedule of events (Appendix F).

Participants randomized to the ESG group will follow the same follow-up schedule as control participants in Level 1. Participants will receive \$100 for every 4 visits they attend consecutively in Level 1 with the ability to earn a maximum of \$300 at the end of the first 12 months of Level 1. In Level 2, participants will report for 6 visits, with the potential to earn \$100 for every 2 consecutive visits they attend. If they attend all 6 visits, they will receive a bonus of \$300 at the final visit, for a potential total earned of \$900 for all visits across two years.

Participants will return for follow-up visits per the schedules of events below (Appendix F). An in-window visit will be considered as reporting for follow-up visits within a two-week window of the visit date.

